#### **Visit 1 (Baseline, in-person visit):**

- All participants will receive patient education regarding osteoarthritis, its natural history, and common treatments.
- All will receive education about the Rx3 Home Exercise Program, which serves as a physical intervention for pain management.
- All participants will be asked to perform the Rx3 Home Exercise Program 3 times weekly.

- All participants will be assigned a study ID# and will be given the on-line baseline Knee injury and Osteoarthritis Outcome Score (KOOS), Short Form-12 (SF-12), and Five Facet Mindfulness Questionnaire-15 (FFMQ-15) surveys using Google Forms or Survey Monkey.
- All participants will receive instructions per the randomization instructions above.
- All participants will be given a Medication Diary to complete on a weekly basis.

**Weeks 2-11:**

Participants will receive **weekly** reminders (via email) asking that they use the app throughout the week. They will also be asked to fill out a short Weekly Survey inquiring:

- Frequency and minutes used for the intervention (My Water Balance and Mindfulness app 10 minutes per day/5 days per week)
- Frequency and minutes spent performing the Rx3 Home Exercise Program in the past week (3 times weekly)
- Use of NSAIDs or other over-the-counter pharmacologic methods of pain control in the past week.

**Visit 2 (Week 12, electronic contact):**

Participants will complete the following surveys and asked the following questions via Google Forms or Survey Monkey. These anonymous forms will be completed via Google Forms or Survey Monkey and the results transcribed to a master excel file for centralized data tracking. Each subject will use their pre-assigned study code to record on each completed questionnaire:

- KOOS
- FFMQ15
- SF-12
- 12-Week survey to evaluate for treatment response to the Rx3 Home Exercise Program and mindfulness app intervention.
- Group 1 (intervention group): Following completion of the 12-week intervention period, participants will no longer have free access to the Headspace application.
- Group 2 (control group) will be asked to cease the use of the My Water Balance application.

**Visit 3 (Week 26, electronic contact):**

Participants will complete the following surveys and asked the following questions via Google Forms or Survey Monkey:

- KOOS
- FFMQ15
- SF-12
- Groups will be queried on their continued use of the Rx3 Home Exercise Program, and over-the-counter analgesic use.
- Group 1 (intervention group) will be queried on continued employment of mindfulness techniques.
- Group 2 (control group) will be queried on continued use of diet and exercise techniques.

**Visit 4 (Week 52, electronic contact):**

Participants will complete the following surveys and asked the following questions via Google Forms or Survey Monkey:

- KOOS
- FFMQ15
- SF-12
- Groups will be queried on their continued use of the Rx3 Home Exercise Program, and over-the-counter analgesic use.
- Group 1 (intervention group) will be queried on continued employment of mindfulness techniques.
- Group 2 (control group) will be queried on continued use of diet and exercise techniques.

**Visit 5 (Week 104, electronic contact):**

Participants will complete the following surveys and asked the following questions via Google Forms or Survey Monkey:

- KOOS
- FFMQ15
- SF-12 Groups will be queried on their continued use of the Rx3 Home Exercise Program, and over-the-counter analgesic use.
- Group 1 (intervention group) will be queried on continued employment of mindfulness techniques.
- Group 2 (control group) will be queried on continued use of diet and exercise techniques.

Weekly survey data will be obtained using the unique participant identifier. At no time will participants use identifiable information when completing these online surveys. These surveys will be conducted using Google Forms or Survey Monkey, and the results transcribed to a master excel file for centralized data tracking. This excel file will be password protected and stored on an encrypted drive on a CAC-enabled computer in a location separate from the participant identifiable information list discussed above. Likewise, results of interval surveys at 0-, 12-, 26-, 52-, and 104-weeks will be obtained using Google Forms or Survey Monkey and identified only via participants' unique identifier.

Study participants will receive 3 reminders asking them to complete their end-of-intervention study surveys; if they do not respond, they will be removed from the study. Those who did not complete the prior set of studies will not be queried for subsequent ones. Use of the mindfulness smartphone app will subsequently be discontinued and the license terminated at the conclusion of the study.

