**a. Interventions and Observations:**

Participants will be re-surveyed at 12, 26, 52, and 104 weeks to evaluate long-term outcomes. The primary outcome measure will be post-intervention change in Knee injury and Osteoarthritis Outcome (KOOS) pain subscale. Secondary outcomes will include the other KOOS subscale scores, FFMQ outcomes, and SF-12 self-reported mental and physical health self-assessments at these same time intervals.

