### Statistical Analysis:

Using an intention-to-treat paradigm, the first primary aims will be statistically compared via one-way analysis of variance (ANOVA). The second primary aim will be statistically compared via two-way analysis of variance (ANOVA).

Missing primary outcome data will be acknowledged in the overall report of analysis. The primary outcome data is based on KOOS scoring system. Per the validated instructions of KOOS analysis, "as long as at least 50% of the subscale items are answered for each subscale, a mean score can be calculated. If more than 50% of the subscale items are omitted, the response is considered invalid and no subscale score should be calculated." In the event that the KOOS data is omitted, the participant will be regarded as a "drop out" and they will be included as such in the intent-to-treat analysis.

Subgroup analyses will be completed via 2-way ANOVA, stratified by FFMQ-15 and SF-12 scores. Subgroup analysis based on age, gender, comorbid behavioral health conditions, and duration of Knee OA symptoms may be considered.

Over-the-counter pharmacologic treatment of musculoskeletal pain is a common practice; given the near ubiquitous usage of these medications, this protocol does not preclude use of NSAIDs or acetaminophen. However, medication use will be monitored via weekly surveys and analyzed post-hoc as a potential confounder of the collected data.

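### The survey stop rule turns a missed week-12 round into permanent loss at weeks 26, 52 and 104, and the plan names no method for a participant without a KOOS score

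*Combined protocol and SAP*

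**What the plan says.** Section 3 schedules KOOS, FFMQ-15 and SF-12 at baseline and four later rounds: "results of interval surveys at 0-, 12-, 26-, 52-, and 104-weeks will be obtained using Google Forms or Survey Monkey". The procedures table under Source of Research Material likewise counts five KOOS surveys per participant. Between baseline and week 12 there is only a weekly form ("They will also be asked to fill out a short Weekly Survey inquiring"), and its listed topics are app use, home exercise and over-the-counter analgesics, not KOOS.

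After the Visit 5 text, the protocol gives the rule for non-response. Participants get three reminders for the end-of-intervention surveys, and "if they do not respond, they will be removed from the study". The next sentence reads: "Those who did not complete the prior set of studies will not be queried for subsequent ones".

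Section 3a defines the endpoint: "The primary outcome measure will be post-intervention change in Knee injury and Osteoarthritis Outcome (KOOS) pain subscale". It places the secondary outcomes at the same follow-up times. No week is named for the primary outcome; I infer week 12, the end of the intervention, from the reference to the post-intervention change.

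Section 6 (Outcome Measures and Statistical Analysis) adopts an intention-to-treat paradigm with a one-way ANOVA for the first aim. On missing data it says "Missing primary outcome data will be acknowledged in the overall report of analysis", and that a participant whose KOOS data are omitted counts as a drop-out: "they will be included as such in the intent-to-treat analysis". It also quotes the KOOS scoring instruction: "as long as at least 50% of the subscale items are answered for each subscale, a mean score can be calculated".

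**The concern.** Someone who skips one electronic survey has not necessarily left the trial. The rule treats them as if they had, so intermittent non-response becomes permanent. Section 3a says the later rounds exist to evaluate long-term outcomes, and the rule reduces what those rounds can show. It also removes the later scores that could indicate whether week-12 non-responders differ from responders.

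The two sections also pull against each other. Section 3 takes the non-responder out of the study; Section 6 puts the same person into the intention-to-treat analysis. A one-way ANOVA of change cannot include someone who has no change score unless a value is supplied, and none is specified. The 50% rule covers partly completed subscales, not an unreturned questionnaire. The method could therefore be settled after results are seen. What is at stake is possible bias of unknown direction.

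**Working it through.** **What a week-12 non-responder contributes.** KOOS is collected at weeks 0, 12, 26, 52 and 104. Missing week 12 leaves one score, the baseline, and the rule closes the other three occasions. Nothing in the protocol reopens follow-up.

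**Two readings of the rule.** The sentence follows one about the end-of-intervention surveys. Read narrowly, it applies only to those who miss week 12. Read broadly, it applies after any missed round. Both end follow-up for the week-12 non-responder.

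**Inputs.** 360 participants and 25% dropout (Sample Size Estimation/Power Analysis); 96 of 120 completing per site, so 1 − 96/120 = 20% loss (Number of Subjects). The plan's first-aim allowance reproduces: 74/(1 − 0.25) = 98.7, or 99 per group. The 180 per group matches 20% loss (144/0.80 = 180), not 25% (144/0.75 = 192), so I carry both rates. The documents do not say when loss occurs; the timings below are assumptions.

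**Rounds not sent, loss spread evenly over four rounds.**
- 25% total: 1 − 0.75^(1/4) = 0.0694 per round. Losses from 360 are 25.0, 23.2, 21.6 and 20.1. Narrow: 25.0 × 3 = 75. Broad: 25.0 × 3 + 23.2 × 2 + 21.6 × 1 = 143.
- 20% total: 1 − 0.80^(1/4) = 0.0543 per round. Losses are 19.5, 18.5, 17.5 and 16.5. Narrow: 19.5 × 3 = 59. Broad: 19.5 × 3 + 18.5 × 2 + 17.5 × 1 = 113.

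**Rounds not sent, all loss by week 12** (the two readings coincide).
- 25%: 0.25 × 360 = 90 people; 90 × 3 = 270.
- 20%: 0.20 × 360 = 72 people; 72 × 3 = 216.

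**What the undefined method can do at week 12.** Take the plan's 10-point difference as the difference among responders, with equal loss L in each arm. Responders-only gives 10. Zero change for drop-outs gives 10 × (1 − L): 9.5 at 5.4% loss, 9.3 at 6.9%, 8.0 at 20% and 7.5 at 25%. If loss were unequal, say 35% in the app arm and 15% in control, zero change gives 0.65 × (10 + c) − 0.85 × c, where c is the mean improvement of control responders: 6.5, 5.5 or 4.5 for c = 0, 5 or 10. With the rates reversed it gives 8.5, 9.5 or 10.5. The unequal rates are illustrative only.

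**Power for the main comparison at 25% loss (SD 15, two-sided 5%).**
- Responders-only, 135 per arm, 10 points: SE = 15 × √(2/135) = 1.83; power over 99%.
- Zero change, 180 per arm, 7.5 points, no change among control responders: app-arm variance 0.75 × 225 + 0.75 × 0.25 × 100 = 187.5 (SD 13.7); control variance 0.75 × 225 = 168.75 (SD 13.0). SE = √((187.5 + 168.75)/180) = 1.41; power about 99.96%.

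**The case against.** The counts are invitations, not answers. They include people who withdrew consent and persistent non-responders. If the same people would never reply, the rule costs almost no data. This stands, and no recoverable fraction can be derived from the documents. It does not justify the rule, because the plan then gives up its chance to find out.

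The sentence may concern week 12 only. That also stands, and is why the narrow figures are given first.

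Four stronger inferences are tempting, and the documents support none of them:
- That the rule distorts the primary result or leaves the main comparison underpowered. It acts after week 12, and the planned ANOVA of week-12 change uses no later score. Power stays above 99% in both cases worked above.
- That 300 to 348 rounds would go unsent. This adds a further 10% loss at each later round to 20% or 25% already lost by week 12. It implies 1 − 0.80 × 0.9³ = 42% or 1 − 0.75 × 0.9³ = 45% total loss, beyond the plan's 20% to 25%.
- That Section 6 permits a responders-only analysis. Its wording promises inclusion and commits to reporting missing data. The gap is that inclusion comes without a method.
- That one particular imputation scheme is required. Several methods would close the gap.

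**Conclusion.** The point holds in limited form and should be fixed. On either reading, a week-12 non-responder keeps only a baseline KOOS and is never asked again, which conflicts with the intention-to-treat paradigm and weakens the long-term secondary outcomes. Under even loss, about 59 to 75 rounds (narrow) or 113 to 143 (broad) are not sent; if all loss comes by week 12, 216 to 270. These figures rest on the plan's 20% to 25% loss and on assumed timing, and they are ceilings on the data recoverable under each timing.

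The second point is that Section 6 includes participants without a KOOS score by declaration only. With equal loss and a 10-point difference among responders, zero change would move the estimate from 10 to between 9.5 and 7.5. The expected conclusion of the main comparison survives, but the reported effect depends on a choice the plan has not made. That week 12 is the primary time point is my inference.

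**What to change.** **Section 3.** Delete removal from the study for survey non-response, and delete the sentence that stops later surveys. State that the week 12, 26, 52 and 104 surveys go to every randomised participant who has not withdrawn consent, whether or not an earlier round was returned.

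**Section 6.** Name week 12 as the primary time point, if that is what is meant. Replace the drop-out wording with one primary missing-data method that keeps all randomised participants in their assigned arm. Multiple imputation by arm, using baseline and any later scores, is one acceptable choice. Add one sensitivity analysis for missing-not-at-random loss that varies the assumption in both arms, since the direction of bias is unknown. Report week-12 loss by arm.

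**Cost.** A wording amendment to two sections, and a check that the consent form agrees. On the loss figures above, about 59 to 270 further electronic rounds with reminders, each carrying KOOS, FFMQ-15, SF-12 and the follow-up questions, plus transcription of those returned into the master Excel file. Some people will receive up to three further rounds of requests that they do not answer. The analysis needs modest extra work. No additional participants or in-person visits are needed.

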**a. Interventions and Observations:**

Participants will be re-surveyed at 12, 26, 52, and 104 weeks to evaluate long-term outcomes. The primary outcome measure will be post-intervention change in Knee injury and Osteoarthritis Outcome (KOOS) pain subscale. Secondary outcomes will include the other KOOS subscale scores, FFMQ outcomes, and SF-12 self-reported mental and physical health self-assessments at these same time intervals.

**b. Setting:**

Active Duty members and DoD beneficiaries ages 18-74 years will be recruited at Scott AFB O'Fallon Family Medicine Residency Clinic located at [name] and Scott AFB Family Health Clinic on-base, David Grant Medical Center [name], at Travis AFB, and Mike O'Callaghan Federal Medical Center, [name] at Nellis AFB. No special populations (e.g., pregnant women, children, military basic trainees, prisoners, detainees) will be recruited.

**c. Date(s):**

February 2019-February 2022

**d. Subjects:**

Adults ages 18-74 with symptomatic knee osteoarthritis. All potentially eligible patients will be offered an opportunity to participate. Some patients may be patients of the PI or AI; however, they will have the research team recruit their patients to prevent any misconception of coercion or undue influence.

**e. Inclusion/Exclusion Criteria:**

Inclusion Criteria	
 
• Male and female Active Duty members and DoD beneficiaries ages 18-74 years
 
• Meet criteria for symptomatic knee osteoarthritis according to the American College of Rheumatology (pain on more than half of the days of the past month during at least one of the following activities: walking, ascending or descending stairs, standing upright, or lying in bed at night)
 
• Demonstrate radiographic evidence of OA, with Kellgren and Lawrence (KL) Grade <math>\geq 1</math> as determined by Lead Site Investigator at each study location
 
• Must have access to a smartphone with enough memory to download the app My Water Balance or the Mindfulness app
 

Exclusion Criteria	
 
• Intra-articular corticosteroid injection in the 3 months prior to participation in the study.
 
• Intra-articular hyaluronic acid/PRP injection in the 6 months prior to participation in the study
 
• Medical condition contraindicating moderate aerobic exercise as determined by their physician
 
• History of knee surgery in the past 6 months or previous knee arthroplasty
 
• Inflammatory joint disease.
 
• Current Practice of Mindfulness
 
• Non-English-speaking
 
• Currently pregnant or planning pregnancy over the study period
 
• Enrollment in other clinical research study during the study period
 
• Inability to comply with treatment protocol, including participation in the Rx3 Home Exercise Program.
 

**f. Source of Research Material:**

Will you be using private information in this study?

Yes

If Yes

protected health information (PHI) held by a covered entity

Use of identifiers with private information						
Identifiers to be Used?	Column A- Looked at by research team	Column B- Recorded on enrollment log, subject list, or key list	Column C- Recorded on data collection tool (survey, spreadsheet, etc.)	Column D- Recorded on specimen containers	Column E- Shared w/ others not on research team	Column F- Stored after study ended
Names						
Study codes linked to individuals' identities using a key only accessible by the researcher						
Phone/Fax Numbers						
E-mails						
DoD ID#						
Coding Plan?						
Describe the method that will be used to create and assign unique study codes to data.	The unique study code will be assigned consisting of a location identifier ("S" for Scott AFB, "N" for Nellis AFB, "T" for Travis AFB), first letter of their first name, the first letter of their last name, and the last four digits of their cell phone number. The code will be placed in a Master Key of identifiable PHI/PII for each subject at each collaborating site.					
Describe the method that will be used to create and assign unique study codes to specimens.	 N/A, not collecting specimens					
What is the format of the key?	 Electronic					
Who will have access to the key?	Research Coordinator at each study site.					
Where will the key be stored and how will it be protected?	
Location(s): Each collaborating site will maintain a Master Key of identifiable PHI/PII that will be kept in an electronic database, which will be encrypted, password protected and the access will be restricted to the Research Coordinator. The Master Key will be electronically stored separately from the coded de-identified research data. The Master Key will not be stored on any non-government or personal computers or laptops. At the conclusion of the study, the data from each site will be de-identified prior to review and analysis.
 
Confidentiality measures: The coded research data will be kept in a locked cabinet in a locked office and only the research department has the key. The coded research data will be retained until the conclusion of the research study. Once a Final Report has been approved by the IRB, all the paper records will be de-identified and any key linking the subject to their records will be destroyed, based on AFI 33-332, "The Air Force Privacy and Civil Liberties Program" and the National Institute of Standards and Technology Special Publication (NIST SP 800-88) for the approved methods to destroy PII. The anonymized research data will not be utilized for further research activity beyond the protocol stipulations without additional IRB approval.
					
Complete the table.						
	Source of Research Material per Participant (Procedures)	# Routine Care	# Research Driven	# Total Procedures		
	Patient Education	1	0	1		
	Mindfulness App usage (intervention group)	0	90	90		
	My Water Balance (Placebo) App usage (control group)	0	90	90		
	Study Diary	0	1	1		
	Rx3 Home Exercise Program (all groups)	0	36	36		
	KOOS Survey	0	5	5		
	FFMQ-15 Survey	0	5	5		
	SF-12 Survey	0	5	5		
g. Instrumentation:						

The KOOS is a validated patient-reported outcome survey designed to assess an individual's perception of their knee pain and associated disability. The SF-12 is a validated assessment of an individual's perception of their physical and mental health-related quality of life. The FFMQ-15 is designed to provide a quantitative evaluation of mindfulness. The Rx3 (rehab, refit, return to duty) Home Exercise Program (which serves as a physical intervention for pain management) is a rehabilitation program designed to treat generalized knee pain.

#### 4. HUMAN SUBJECT PROTECTION

##### Recruitment and Consent Processes:

All potentially eligible patients will be offered an opportunity to participate. Participants will be recruited from Family Medicine, Internal Medicine, Orthopedics, and Sports Medicine clinics by way of flyers in the clinic areas, hospital at large, and in community boards at public venues on post (Commissary, BX, etc.). Some patients may be patients of the PI or AI; however, they will have the research team recruit their patients to prevent any misconception of coercion or undue influence. When a potential subject is identified by the treating physician, the Research Staff will be contacted to speak with the patient directly, with prior verbal or written authorization by the patient. Hospital staff will ask the patient if they are willing to speak with the research staff and, if they agree, then the research staff will be contacted to come to the clinic and discuss the study with the potential participant. Advertisements will be posted around the base. Pregnant women will be excluded from the study as they experience a shift in their center of mass and a progressive weakening of their abdominal muscles, both of which contribute to knee pain outside the scope of this study.

##### Consent Processes:

Informed Consent and HIPAA authorization will be sought in advance of any screening and study-related procedures from each prospective study subject and appropriately documented in accordance with 32 CFR 219.117. Potential candidates will be notified about the study either through posted advertisements or by their healthcare provider and will be given the opportunity to consent by one of the referred study coordinators. The study coordinator will provide a written copy of the Informed Consent Document (ICD). The subject may decline to consent without prejudice. At the subjects' discretion, they may take the ICD home to discuss further with family members or another physician, prior to making a decision. If they decide they are interested in participating in the study, they can contact the research department. If the subject consents, a copy of the signed ICD and HIPAA Authorization Document will be given to the subject. No vulnerable populations are included in this research study. Subjects who cannot provide Informed Consent will not be allowed to participate. No Legally Authorized Representatives (LAR) will be utilized. Each subject will be asked to place their de-identified research data into the "Mike O'Callaghan Military Medical Center General Research Data Repository" (FWH20180064H) for future research. If the subject does not give their authorization, then the de-identified research data will be destroyed no later than 3 years following the closure.

